5.4 Exploratory Endpoints

GMTs of total binding IgG antibody against the SARS-CoV-2 index virus will be summarized at baseline and post-baseline time points for ABNCoV2 and Comirnaty in subsets of each Part A cohort.

Immunogenicity of ABNCoV2 and Comirnaty will be explored as the geometric mean fold increases from baseline to each scheduled post-baseline time points in:

- Neutralizing antibodies against the SARS-CoV-2 index virus.
- Neutralizing antibodies against the SARS-CoV-2 VOCs circulating at time of the trial.
- Total binding IgG antibodies against the SARS-CoV-2 index virus (in subsets of each Part A cohort).

ABNCoV2		Clinical Trial Protocol
ABNCoV2-03	Edition 8.0	

In addition, the kinetics of neutralizing antibody responses over time for ABNCoV2 and Comirnaty will be explored by calculating GMTs of neutralizing antibodies against the SARS-CoV-2 index virus and VOCs circulating at time of the trial at 1, 4, 13, and 26 weeks after trial vaccination in subsets of the Part A cohorts.

Cellular immune responses at 1 week after vaccination with ABNCoV2 within the immunogenicity subsets of each Part B cohort will be explored by calculating the geometric means of SARS-CoV-2-specific T cells secreting interferon- γ and interleukin-4 upon restimulation, as measured by ELISpot.

6 Study Population

6.1 Inclusion Criteria

Subjects must meet all the inclusion criteria listed in the Synopsis (Section 1.3) to be enrolled in either Part A or Part B of the trial.

6.2 Exclusion Criteria

The criteria that will exclude subjects from eligibility for both Parts A and B of the trial are provided in the Synopsis (Section 1.3).

6.3 Inclusion of Older Subjects

Sites will be instructed to pursue a target of 25% of enrollment to be subjects that are \geq 65 years of age for Part A and 33% to be \geq 65 years of age for Part B. The end goal is to have at least 1000 subjects \geq 65 years of age who receive ABNCoV2.

6.4 Selection of Subjects

The investigator will keep a log of subjects screened for the trial and will provide the reason in case of exclusion. Information about every screened subject will be documented in the electronic case report form (eCRF).

For subjects who enter screening but do not proceed to vaccination, the information documented in the eCRF will be limited to the date of informed consent form (ICF) signature, demographics, and reason for screen failure, including any (S)AEs that led to the screen failure.

6.5 Recruitment and Retention

Subjects will be actively recruited. Recruitment strategies, including advertisements approved by the Independent Ethics Committee (IEC) and Institutional Review Board (IRB), will be evaluated by the Sponsor.

ABNCoV2		Clinical Trial Protocol
ABNCoV2-03	Edition 8.0	

Individuals identified as potential subjects for the trial will be provided with all the necessary information required to make an informed decision about their participation.

7 Study Intervention

7.1 Vaccine Dosage and Administration

In Part A, each subject will be randomized to receive 1 dose of 100 μ g ABNCoV2 vaccine or 1 adult boost dose of 30 μ g Comirnaty (tozinameran, BNT162b2) vaccine. An unblinded member of the local site team will handle the trial vaccine, while the subject and the staff involved in subject evaluation and follow-up will remain blinded. In case of an emergency that makes unblinding necessary (i.e., the subject's safety is dependent on unblinding), a mechanism that permits rapid unblinding but does not permit undetectable breaks of the blinding will allow the Investigator the possibility of learning the treatment assignment for a subject. The detailed process for emergency unblinding will be described in a trial-specific procedure.

In Part B, all subjects will receive the same single dose of 100 μ g ABNCoV2 as in Part A but as an open-label trial vaccination. All vaccinations will be administered at the investigational sites and injected intramuscularly into the deltoid muscle of the non-dominant arm.

7.2 Subject Discontinuation

A subject may be discontinued early from the active trial phase or the overall trial for different reasons. Reasons for early discontinuation of a subject may include, but are not limited to:

- Clinical need for or receipt of concomitant or ancillary therapy not permitted in the trial as outlined in Section 11.4.
- Subject's receipt of an approved booster vaccination for SARS-CoV-2 outside the protocol.
- Subject's request to discontinue (withdrawal of consent to participate).
- Subject unwilling or unable to comply with trial requirements.
- Any reason that, in the opinion of the investigator, requires or supports early discontinuation of a subject.

Each subject has the right to terminate their trial participation completely at any time for any reason, and the investigator may also terminate a subject's trial participation. Subjects whose trial participation is terminated during the active trial phase of either Part A or Part B should undergo a concluding end of active phase (EAP) visit, including safety laboratory testing and pregnancy test for women of childbearing potential (WOCBP). The subject has the right to refuse the EAP visit; however, the clinical trial site (CTS) should make every effort to collect any safety data possible for the subject. If the subject is willing, the 2-month follow-up (FU) phone call (FU1), the 3-month FU visit (FU2), and/or the 6-month visit (FU3) should still be performed to collect

ABNCoV2		Clinical Trial Protocol
ABNCoV2-03	Edition 8.0	

any potential SAEs/AESIs which occurred after vaccination. Subjects who discontinue after receiving trial vaccine will not be replaced.

8 Schedule of Procedures by Visit

The trial procedures will be conducted according to the trial procedure schedule (Section 1.4) and as described on the following pages. Visits must be scheduled within the protocol-allowed visit windows.

8.1 Screening Visit

All subjects must be thoroughly informed about all aspects of the trial (e.g., trial visit schedule, required evaluations and procedures, risks and benefits) as described in the ICF. Written informed consent must be obtained according to local requirements before any trial-related assessments may be carried out.

After the written informed consent has been obtained, subjects will enter a screening period of up to 14 days before the trial vaccination. Screening procedures are listed in the trial procedure schedule in Section 1.4.

If a subject has been screened and cannot be vaccinated because of a certain transient condition (e.g., abnormal lab value due to an acute condition or a missing lab evaluation due to mishandling of the sample), the respective test(s) should be repeated. The re-test must be performed, and eligibility determined within the 14-day window started by the initial screening visit.

If a subject cannot be vaccinated due to other circumstances (e.g., completion of a wash-out period for a medication or vaccine not allowed during the trial) leading to a delay over the 14-day window, a complete re-screening must be performed, and a new subject number will be assigned. The clock then re-starts at the new screening visit within 14 days before randomization. A subject may be fully re-screened only once.

8.2 Active Phase

8.2.1 Visit 1

After successfully passing the screening evaluations, the eligible subjects for Part A can be randomized and vaccinated with ABNCoV2 or Comirnaty, no later than 14 days after the start of screening. Eligible volunteers for Part B can be vaccinated with ABNCoV2, again no later than 14 days after the start of screening. The procedures performed at Visit 1 are listed in the trial schedule in Section 1.4. With respect to timing, procedures listed above the randomization event in the trial schedule should be performed prior to randomization and vaccination; of greatest importance is that collection of samples for serum antibody titers, PBMC testing, and

ABNCoV2	Clinical Trial Protocol
ABNCoV2-03	Edition 8.0

nucleocapsid protein antibody testing must always be performed prior to vaccine administration. Refer to Section 12.1 for randomization procedures.

Investigational sites will be provided with instructions for administration of trial vaccine. Subjects will be observed for 30 minutes after vaccine administration, and AEs that occur immediately following trial vaccination will be collected. The site coordinator also will give the memory aid (along with appropriate instruction) to subjects at Visit 1 for them to record any solicited AEs that occur after vaccination, for a period of 8 days (the day of vaccination and the next 7 days).

8.2.2 Visit 2

Visit 2 is to occur 5 to 7 days after trial vaccination. The procedures performed at Visit 2 are listed in the trial schedule in Section 1.4. Core procedures performed in the active phase visits following trial vaccination include the evaluation of vital signs, recording of concomitant medications, targeted physical examination, and AE recording. Blood samples are collected for serum antibody titers from subjects in Part A and for PBMCs from subjects in the Part B immunogenicity subset.

Subjects are asked if they have any SARS-CoV-2 symptoms or tested positive between Visit 1 and Visit 2, and if so, responses will be recorded as AEs. A SARS-CoV-2 infection polymerase chain reaction (PCR) test may be performed if it is determined to be clinically indicated.

As Visit 2 is the first visit following trial vaccination, site personnel are to examine the injection site and review the memory aid with the subject. Expected injection site reactions are to be recorded by the subject with solicited AEs on the memory aid. Unexpected findings are to be recorded by site personnel as AEs. All completed pages of the memory card are collected. If there are any symptoms that have not yet resolved the site should counsel the subject regarding continued collection of symptoms using the memory aid.

8.2.3 Visit 3

Visit 3 is to occur 2 weeks after trial vaccination, ± 2 days. The procedures performed at this visit are listed in the trial procedure schedule in Section 1.4. In addition to the core set of trial procedures listed above, a blood draw is performed at this visit for safety labs in all subjects, and for serum antibody titers and nucleocapsid protein antibody testing in Part A and in the Part B immunogenicity subset. The subjects are asked if they have any SARS-CoV-2 symptoms or tested positive since the last visit. If there were any unresolved solicited symptoms at the prior visit, the memory aid is reviewed with the subject and all completed pages collected.

ABNCoV2		Clinical Trial Protocol
ABNCoV2-03	Edition 8.0	

8.2.4 Visit 4 / End of Active Phase

Visit 4 is the last visit in the active phase of both parts of the trial, and it occurs 4 to 5 weeks after trial vaccination. As shown in Section 1.4, the core trial procedures are performed at this visit, a final pregnancy test is done for WOCBP, and blood is collected for serum antibody titers in Part A. The subjects are asked if they have any SARS-CoV-2 symptoms or tested positive since the last visit. If there were any unresolved solicited symptoms at the prior visit, the memory aid is reviewed with the subject and all completed pages collected.

8.3 Follow-up Phase

To monitor safety and immunogenicity, all subjects will receive 1 phone call at 2 months (FU1, days 56 to 70) and attend 2 visits, at 3 months (FU2, days 91 to 105) and 6 months (FU3, days 182 to 196) after trial vaccination. The phone call involves collection of AESIs and SAEs only. For the follow-up visits, as shown in the trial schedule in Section 1.4, the core procedures from the active phase are repeated, including collection of MAAEs, AESIs, and SAEs, but concomitant medications and other AEs are no longer recorded, and blood collection for serum antibody and nucleocapsid protein testing occurs only in Part A. The subjects are asked if they have any SARS-CoV-2 symptoms or tested positive since the last visit. The memory aid may be collected at the FU2 visit if not collected previously and all symptoms have resolved. At the FU3 visit, the memory aid will be collected regardless of ongoing symptoms for recording.

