	 18. Chronic systemic administration (defined as more than 14 days) of >5 mg prednisone (or equivalent)/day, or any other immune-modifying drugs during a period starting 3 months prior to administration of the vaccine and ending 4 weeks after vaccination. The use of topical, inhaled, ophthalmic and nasal glucocorticoids is allowed. 19. History of organ transplantation, whether or not accompanied by chronic immunosuppressive therapy. 20. Administration or planned administration of immunoglobulins and/or any blood products during a period starting 3 months prior to administration of the vaccine and ending 4 weeks after vaccination. Receipt of packed red blood cells given for an emergency indication in an otherwise healthy person, and not required as ongoing treatment is not exclusionary (for example packed red blood cells given in emergency during an elective surgery). 21. Use of any investigational or non-registered drug or vaccine other than the trial vaccine within 30 days preceding the administration of trial vaccine, or planned administration of such a drug or vaccine throughout the trial. 22. Involvement in this trial as site personnel. 23. Known bleeding disorder that, in the opinion of the investigator, would contraindicate intramuscular injection.
Trial Population: Inclusion of Subjects ≥65 Years of Age	Sites will be instructed to pursue a target of 25% of enrollment to be subjects \geq 65 years of age in Part A and 33% of enrollment to be subjects \geq 65 years of age in Part B. The target is to have approximately 1000 subjects \geq 65 years of age who receive ABNCoV2.

DocuSign Envelope ID: B668B9DC-A299-48F2-8894-D0352DD0D3C2

ABNCoV2

ABNCoV2-03

Edition 8.0

Clinical Trial Protocol

0
5
-
3
70
_
- E
F .
+
۱

Visit	SCR	V1	V2	V3	V4/	FUI	FU2	FU3
					EAP	(phone)		
Day / Visit + Days	V1 -141	Day 1	V1ª +5-7	V1 ^a +12–16	V1 ^a +28–35	$V1^{a} + 56 - 70$	$V1^{a}$ +91–105	V1 ^a +182–196
Target week	-2	0	-	2	4	8	13	26
Target month		0			1	2	3	6
Informed consent	Х							
Eligibility assessment	Х	X						
Demographics collection	Х							
Medical history review	Х							
Physical examination (including height, weight, BMI) ^b	Х							
ECG ^b	Х							
Evaluation of vital signs ^b	Х	Х	х	Х	Х		Х	Х
Recording of prior and concomitant medication	Х	Х	X	X	Х			
Blood draw for safety labs ^b	Х			Х	(X) ^c			
Pregnancy test for WOCBP ^d	Х	Х			Х			
Counseling on avoidance of pregnancy for WOCBP ^e	Х	Х						
Hep-B, HCV, HIV test	Х							

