11.4 Prohibited Medications

Prohibited medication or medication where washout periods need to be adhered to are (see also eligibility criteria in the Synopsis [Section 1.3]):

- Administration of any SARS-CoV-2 vaccine other than the trial vaccine for the entire trial period.
- Vaccination with any licensed live vaccine within 30 days prior to or after trial vaccination or any licensed non-live vaccine within 14 days prior to or after trial vaccination.

ABNCoV2		Clinical Trial Protocol
ABNCoV2-03	Edition 8.0	

- Chronic systemic administration (defined as more than 14 days) of >5 mg prednisone (or equivalent) per day or any other systemic use of immune-modifying drugs during a period starting 3 months prior to administration of the trial vaccine and ending at the last visit of the active trial phase. The use of topical, inhaled, ophthalmic and nasal corticoids will be permitted.
- Administration of immunoglobulins and/or any blood products during a period starting 3 months prior to administration of the trial vaccine and ending at the last visit of the active trial phase.
- Use of any investigational or non-registered drug or vaccine other than the trial vaccine within 30 days preceding the administration of the trial vaccine, or planned administration of such a drug or vaccine during the entire trial period (i.e., through 6 months after the trial vaccination).

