11.9.2 Myocarditis and Pericarditis

Myocarditis and pericarditis are a subset of AESIs of particular interest. Postmarketing data from mRNA vaccine recipients have demonstrated increased risks of myocarditis and pericarditis in males under the age of 40 years following a second dose of mRNA vaccine. Cases have been reported in older males and in females as well, and also following other doses. Available data from short-term follow-up suggest that most individuals have had resolution of symptoms with conservative management, although information is not yet available about potential long-term sequelae.

The spike (S) protein antigen can induce antibodies to SARS-CoV-2 spike glycoproteins that cross-react with myocardial contractile proteins, including myocardial α -myosin heavy chain (Vojdani and Kharrazian, 2020). In contrast to the currently licensed COVID-19 vaccines, the ABNCoV2 candidate vaccine does not contain the full-length S protein of the SARS-CoV-2 virus, but specifically the receptor binding domain (RBD) of the S protein. However, as the pathomechanism for myocarditis or pericarditis following COVID-19 vaccination is not fully understood, and the specific role of the RBD remains unclear, precautionary measures will be implemented for this trial.

Symptoms of myocarditis or pericarditis include chest pain, shortness of breath, or feelings of having a fast-beating, fluttering, or pounding heart, with onset of symptoms most commonly reported within a few days following vaccination. While some cases required intensive care support, available data from short-term follow-up suggest that symptoms resolve in most individuals with conservative management. Information is not yet available about potential long-term sequelae. Subjects will receive educational materials explaining the symptoms of

Bavarian Nordic

ABNCoV2-03

Edition 8.0

myocarditis and pericarditis and instructing them to seeking medical attention if they occur. Subjects reporting acute chest pain, shortness of breath, palpitations, or other signs or symptoms of myocarditis or pericarditis within 4 to 6 weeks after vaccination will be referred to a cardiologist for evaluation and management. Cases of myocarditis and pericarditis will be followed until resolution of symptoms and abnormal test findings.

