**Table 3: Populations for Analyses**

Analysis Set	Definition
Enrolled	All subjects who have signed informed consent.
Randomized	All subjects who are assigned a randomization number in the randomization system.
Safety Analysis Set	All subjects who received a trial vaccination with either ABNCoV2 or Comirnaty.
Immunogenicity Analysis Set (IAS) a	All subjects who are in the Safety Analysis Set, have at least a baseline and 1 post-vaccination neutralizing antibody result, and have neither intercurrent events indicative of SARS-CoV-2 infection nor received a booster for SARS-CoV-2 outside of the trial within 2 weeks of vaccination. If further protocol deviations are found that would have a significant impact on a subject's humoral responses to trial vaccination, decisions on removing these subjects from the IAS will be made prior to locking the database and unblinding for the primary analysis.
Kinetics Analysis Set – 3 Months a	Subset of Part A subjects in the IAS who have neutralizing antibody results for the SARS-CoV-2 index virus at the Week 13 visit (91-105 days after vaccination) and have neither had a SARS-CoV-2 infection by Week 13 nor received a booster for SARS-CoV-2 outside of the trial by Week 13.
Kinetics Analysis Set – 6 Months a	Subset of Part A subjects in the IAS who have neutralizing antibody results for the SARS-CoV-2 index virus at the Week 26 visit (182-196 days after vaccination) and have neither had a SARS-CoV-2 infection by Week 26 nor received a booster for SARS-CoV-2 outside of the trial by Week 26.

aSARS-CoV-2 infection for IAS and the kinetics analysis sets will be determined by subject-reported adverse events of SARS-CoV-2 infection, positive PCR testing, or an increase in nucleocapsid protein indicating COVID-19 infection.

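### The SAP's Week 13 and Week 26 kinetics sets exclude subjects boosted outside the trial, but no contact after Visit 4 is scheduled to ask about or record an outside SARS-CoV-2 vaccine

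*Protocol*

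**What the plan says.** The row "Recording of prior and concomitant medication" in the protocol's Trial Schedule (Section 1.4) is marked from Screening to V4/EAP and is blank at FU1, FU2 and FU3. The schedule in SAP Appendix 1 is the same. Section 8.3 agrees: at FU2 and FU3 the core procedures continue, "but concomitant medications and other AEs are no longer recorded".

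For the contacts that remain, Section 8.3 says of FU1: "The phone call involves collection of AESIs and SAEs only". For the visits it says: "The subjects are asked if they have any SARS-CoV-2 symptoms or tested positive since the last visit". Neither mentions vaccination.

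Section 11.4 prohibits this for the whole of follow-up: "Administration of any SARS-CoV-2 vaccine other than the trial vaccine for the entire trial period". Section 7.2 lists an outside booster among the reasons for which a subject may be discontinued.

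SAP Table 3 limits the 3-month kinetics set to Part A subjects who "have neither had a SARS-CoV-2 infection by Week 13 nor received a booster for SARS-CoV-2 outside of the trial by Week 13". The 6-month set has the same condition at Week 26. The table's footnote lists how infection is determined: adverse events, PCR and nucleocapsid results. It gives no source for boosters.

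**The concern.** An analysis-set exclusion is only as good as the data that trigger it. The SAP (Section 3) explains why this one exists: a further boost would affect the immunogenicity results. Yet the plan stops the routine record that would show such a boost well before the two time points at which the exclusion applies. A subject re-boosted after Visit 4 who does not mention it stays in the set, and the Week 13 or Week 26 titer then reflects a later product as well as the trial vaccine. Durability would look better than it is.

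The same missing information bears on late safety. The entire-trial summaries of SAEs, AESIs and MAAEs run to about Month 6, and the SAP has no rule for events that follow another SARS-CoV-2 vaccine.

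**Working it through.** The plan states no figure on this point, so there is none to reproduce. The check is a trace through the text, then the length of the gap, then an illustration of size.

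**1. Could another assessment reveal an outside booster after Visit 4?**
- Protocol 11.3 requires concomitant medication to be recorded but sets no end date. The schedule and 8.3 set it at V4/EAP.
- Nucleocapsid testing at FU2 and FU3 detects infection. SAP 4.8 notes that current vaccines do not contain that protein, so the test cannot show a booster.
- The MAAE definition (11.1.5) leaves out routine visits for vaccination.
- The minimum content of an SAE/AESI report (11.14.1) covers trial medication and no other vaccine.
- Protocol deviations are recorded by the site (16.2) and databased and listed (SAP 4.6.3), and discontinuation reasons are collected. Both work only if the site learns of the vaccine.

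Some capture therefore exists, but it is passive.

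**2. Length of the gap.** Visit windows in days after vaccination: V4 28–35, FU2 91–105, FU3 182–196.
- To Week 13: 91 − 35 = 56 to 105 − 28 = 77 days.
- To Week 26: 182 − 35 = 147 to 196 − 28 = 168 days. As a share of the time to FU3, 147/182 = 81% and 168/196 = 86%.
- Week 2 (V3, days 12–16) falls before V4, while concomitant medication is still recorded.

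**3. Possible size.** If a share f of an arm has an undetected k-fold rise, the mean log10 titer moves by f × log10(k), so the GMT is multiplied by k^f. For example, with f = 0.10 and k = 7.1: 0.10 × 0.851 = 0.085, and 10^0.085 = 1.22.

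The documents give no rate, so f = 5%, 10% and 20% are assumptions. For k, protocol 2.2.2 gives two-week rises after 100 µg ABNCoV2 in phase 2: 2.2-fold where the baseline titer was at or above the median, and 7.1-fold where it was quantifiable but below the median. The 39.7-fold rise applies to subjects below the LLOQ, and the overall 15.1-fold rise includes them. Both are set aside because kinetics subjects were vaccinated in the trial within the preceding six months. Applying these rises to whatever product was given outside the trial is a further assumption.

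| f | k = 2.2 | k = 7.1 |
|---|---|---|
| 5% | 1.04 | 1.10 |
| 10% | 1.08 | 1.22 |
| 20% | 1.17 | 1.48 |

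These are upper-range values, because they treat every affected sample as taken near the post-booster peak.

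**4. Between-arm ratio.** The ratio is multiplied by k_A^f_A / k_C^f_C (A = ABNCoV2, C = Comirnaty). This equals 1 when f and k are the same in both arms.

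**5. Safety and time to infection.** SAP Section 3 summarises safety by the vaccine actually received, and SAP 4.6.8 censors time to COVID-19 infection at the last visit attended. Neither has a rule for an outside vaccine. That would remain so even if every outside vaccine were recorded, so it needs its own SAP rule.

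**The case against.** The plan is not blind to outside boosters. They are prohibited throughout, are a listed discontinuation reason, and count as deviations that reach the database. The eCRF and the trial-specific deviation procedure are not among the documents and may contain a prompt. This stands in part: the exclusion can be applied to boosters that become known, so it would be wrong to call it unworkable. But a prohibition does not find the cases that breach it, and the documents provide no active question.

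A reader might also infer three stronger things that the documents do not support.

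- *That late events are counted against the trial vaccine because recording stops.* They stay in that column because the SAP summarises by vaccine received and has no flagging rule. The endpoint that ignores relationship makes no causal attribution. The related SAE/AESI endpoint needs a causality judgement that weighs other causes, with missing assessments only provisionally set to possible. What can be said is that late judgements lack systematic vaccine data.
- *That late myocarditis would be misattributed.* Section 11.9.2 does say "Postmarketing data from mRNA vaccine recipients have demonstrated increased risks of myocarditis and pericarditis", but the Appendix 4 questionnaire asks for other suspect products, medication dates and alternative causes once a case is reported.
- *That the vaccine comparison is compromised.* Part A operational staff stay blinded at subject level through follow-up (SAP 4.1.3), and the documents give no reason to expect different uptake by arm.

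**Conclusion.** The point holds within a limited scope. As written, the plan has no active ascertainment of outside SARS-CoV-2 vaccines after Visit 4 and no named data source for a booster exclusion that the SAP applies at Weeks 13 and 26. The durability GMTs may therefore keep re-boosted subjects. Under the assumed 5% to 20% undetected share and 2.2- to 7.1-fold rise, an arm's GMT would be inflated by about 1.04 to 1.48 times. That is an illustration at the upper end, not an estimate. The between-arm ratio is biased only if uptake or rise differs by arm.

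The affected kinetics outputs are exploratory and descriptive. The Week 2 primary and key secondary tests, and their power, are untouched. Separately, the entire-trial safety summaries that ignore relationship and the time-to-infection analysis lack a rule for what happens after an outside vaccine. This should be corrected, but it does not threaten the trial's main conclusion.

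**What to change.** - **Protocol 8.3 and Trial Schedule:** at FU1, FU2 and FU3, ask every subject whether any SARS-CoV-2 vaccine was received since the last contact, and record product and date in the eCRF.
- **SAP Table 3:** derive the Week 13 and Week 26 booster exclusions from that field together with deviation and disposition data, and say so in the footnote, as is already done for infection.
- **SAP safety sections:** in the entire-trial SAE, AESI and MAAE summaries, flag events with onset after an outside SARS-CoV-2 vaccine and show counts with and without them. State how time to COVID-19 infection treats follow-up after such a vaccine.

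The cost is one question at three existing contacts, one eCRF field and a few SAP derivations. The eCRF already takes prior SARS-CoV-2 vaccines with dose and dates (11.3). A few more subjects would leave the kinetics sets. If collection can no longer be changed, the SAP can still name deviations and disposition as the source, state that capture is passive, and flag late events after known outside vaccines.
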